7.2.2. Adverse Drug Reaction (ADR)

Adverse Drug Reactions are all AEs considered to have a reasonable causal relationship to the trial medication, as judged by a medically qualified Investigator or the Sponsor. The expression reasonable causal relationship means that there is evidence or argument to suggest a causal relationship.

7.2.3. Serious Adverse Event (SAE)

A SAE is defined as an untoward and unintended response to a study drug (AE) that meets one of the following serious criteria:

- a) Lead to death
- b) Is life-threatening
- c) Requires in-patient hospitalization or prolongations of existing hospitalization
- d) Results in persistent or significant disability/incapacity
- e) Is a congenital anomaly/birth defect
- f) Require intervention to prevent permanent impairment or damage

Medical and scientific judgement should be exercised in deciding whether an event is serious. For example, important medical events that may not be immediately life threatening or result in death or hospitalization, but may jeopardize the subject or may require intervention to prevent one of the other outcomes listed in the definition above. These should also usually be considered SAEs.

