VAR is already tested in subjects with AUD and the interaction with alcohol was found not to be clinical significant (Litten et al., 2013;de Bejczy et al., 2015). In the clinical trials with the combination VAR and BUP, AUD patients have been excluded. However, alcohol-consuming patients were not excluded and alcohol consumption was not an exclusion criteria. No adverse interactions were described (reference studies 1-7 above). Drugs of abuse, including alcohol, enhance DA levels in the brain. Both BUP and VAR increase DA levels in the reward region of the brain. However, BUP and VAR have a slow onset of action and a much lower increase in DA levels and are not judged to have an addictive potential. According to Läkemeldesverket, no reports of addiction to VAR or BUP have been reported (oral communication). The combination of alcohol, VAR and BUP have a theoretical risk of enhancing alcohol's effects and producing a high/false sense of well-being (Volkow and Swanson, 2003), although no such effects were observed in the VAR studies on alcohol. The known increase risks for seizures have been minimized by the exclusion criteria of Epilepsy and alcohol seizures (within 5 years) and need of detoxification. The risk for worsening symptoms of other psychiatric disorders has been minimized by the exclusion criteria. Common side effects of VAR and BUP include e.g. insomnia, dizziness, nausea, all of which are associated with alcohol consumption. These symptoms could possibly be more frequent in the case of VAR, BUP and alcohol in combination.

Risks associated with study specific examinations and sampling

Venous blood will be collected for investigation of eligibility measures and/or outcome measures and/or safety measures at every study visit (9 in total) by professional medical staff (See table 2, section 3.1 for specific investigations). The blood will be drawn from the upper or lower arm. The total amount of blood taken during the whole study will be 245 mL. It is rare for a blood test to result in serious complications but there is a small risk for complications like infections, excessive bleeding, bruising, fainting and dizziness and hematomas. *Action taken to control or minimize above described risks.* Infection control during blood sampling: the medical staff is highly trained and is required to follow the regulations regarding the disposal and storage of needles and blood samples. In rare cases, a wound occurs that become red and swollen, and if

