7.2. Definitions

7.2.1. Adverse Event (AE)

An AE is any untoward medical occurrence in a patient or clinical investigation subject administered a medicinal product and which does not necessarily have a causal relationship with this treatment. An AE can be any unfavorable and unintended sign (including an abnormal laboratory finding), symptom, or disease temporally associated with the use of the IMP, whether or not related to the IMP.

Causality

The Investigator is responsible for determining whether there is a causal relationship between an AE and the use of a medicinal product.

All AEs are categorized either as unrelated, possibly related or related, as defined below:

- Unrelated: the AE is not reasonably in relation to the use of the IMP, or another cause can itself explain the occurrence of the event.
- Possibly related: the AE may be explained by an effect of the IMP and the onset is reasonable in relation to the use of the medicinal product, however there is insufficient information to determine the likelihood of this possibility.
- Related: the AE is most likely explained by the IMP and the onset is reasonable in relation to the use of the medicinal product (see 7.2.2., ADR).

Severity

In addition to assessing the relationship of the administration of the IMPs to adverse events, an assessment is required of the intensity (severity) of the event. The following over-all classification will be used:

- Mild: An adverse event which is relatively mild and transient in nature, but can be an annoyance, and does not interfere with normal activities.
- Moderate: An adverse event which may be uncomfortable but is not hazardous to health. It may be sufficiently discomforting to interfere with normal activities but does not completely prevent them.
- Severe: An adverse event which is incapacitating and/or is a hazard to the subject

Definition of action taken

Action taken will be defined as

- None. No action will be taken
- Due to the AE, interruption in IMP administration
- IMP discontinued. Due to the AE, the patient's IMP administration will be discontinued.
- Trial discontinuation
- Others (like referrals)

Definite event outcome at resolution or End of Trial

- Resolved without sequelae
- Resolved with sequelae
- Not resolved
- Fatal
- Unknown (if lost to follow up)

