7.2.4. Suspected unexpected serious adverse reaction (SUSAR)

A suspected unexpected serious adverse reaction (SUSAR) is a SAE of which nature or severity is not consistent with the applicable product information, that is, the SmPCs for VAR and BUP. A SUSAR may be related or unrelated to the study drug, but is unexpected. The responsibilities and requirements concerning SUSAR reporting are determined by Directive 2001/20/EC and a detailed guidance document (CT-3).

If the natural course of the disease usually causes certain symptoms, hospitalizations, etc., these will not be reported as incident or SUSAR (for example hospitalization due to alcohol intoxication).

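### Section 7.2.3 defines a SAE as a drug response, which contradicts the AE and SUSAR definitions and, read literally, takes serious events judged unrelated out of 24-hour SAE reporting

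*Protocol*

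**What the plan says.** The protocol sets out four linked definitions in section 7.2.

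- **AE (7.2.1).** An AE is an untoward occurrence "which does not necessarily have a causal relationship with this treatment". Causality is then graded: "All AEs are categorized either as unrelated, possibly related or related, as defined below".
- **ADR (7.2.2).** Causality is what separates a reaction from an event: "Adverse Drug Reactions are all AEs considered to have a reasonable causal relationship to the trial medication".
- **SAE (7.2.3).** "A SAE is defined as an untoward and unintended response to a study drug (AE) that meets one of the following serious criteria". Six criteria, a to f, follow; in-patient hospitalisation is criterion c.
- **SUSAR (7.2.4).** A SUSAR is introduced as a SAE that does not fit the product information. The section adds: "A SUSAR may be related or unrelated to the study drug, but is unexpected". For events that belong to the usual course of the disease it says "these will not be reported as incident or SUSAR (for example hospitalization due to alcohol intoxication".

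Three reporting rules use these labels. Under 7.3.1 every AE goes on the CRF whatever its attribution. Under 7.3.3 every SAE goes to the sponsor on a SAE form within 24 hours. Under 7.3.5 the annual safety report summarises SAEs and SUSARs.

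**The concern.** Taken at its word, 7.2.3 makes a causality opinion the entry condition for being a SAE. The investigator, blinded to treatment, would settle relatedness first, and only events seen as drug responses would then be tested against criteria a to f.

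This matters more here than in many trials. Section 7.2.1 allows the unrelated grade whenever another cause can account for the event by itself. In patients with alcohol use disorder who are still drinking, alcohol will often be available as that cause.

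The events most exposed are also ones where the sponsor would want early sight of a signal. Section 7.1 says: "The combination of alcohol, VAR and BUP have a theoretical risk of enhancing" the effects of alcohol. It also mentions a few reports of reduced alcohol tolerance with bupropion, and notes that bupropion has had no controlled trial in alcohol-dependent subjects. The interaction risk should not be overstated: the same sentence of 7.1 goes on to say that nothing of the kind was seen in the varenicline studies.

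What is at stake is whether serious events judged unrelated reach the sponsor promptly and are counted as serious.

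**Working it through.** No arithmetic applies and there is no stated figure to reproduce. The check sets the sections side by side.

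1. **AE against SAE.** By 7.2.1 the set of AEs includes unrelated events. The 7.2.3 sentence calls its subject a response to the drug and, in brackets, an AE. The first description excludes unrelated events and the second includes them, so the sentence conflicts with itself and with 7.2.1.

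2. **ADR against SAE.** By 7.2.2 an AE with a reasonable causal link is an ADR. A drug response that meets a seriousness criterion is therefore a serious ADR. Read literally, 7.2.3 defines that narrower class and leaves no term for a serious AE judged unrelated.

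3. **SAE against SUSAR.** By 7.2.4 every SUSAR is a SAE. By 7.2.3 every SAE is a drug response. It follows that no SUSAR can be unrelated, yet 7.2.4 says that one may be. Both statements cannot stand. The 7.2.4 wording also conflicts with the words *suspected* and *reaction* in the term itself.

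4. **Consequence for a serious event judged unrelated, read literally.**
   - CRF entry as an AE (7.3.1): required.
   - SAE form within 24 hours (7.3.3): not required, because the event is not a SAE.
   - Annual safety report (7.3.5): not required, for the same reason.
   - SAE part of the AE/SAE safety variable (Table 4 in 6.1), summarised descriptively by treatment group (8.2): not counted as a SAE.

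5. **Does the CRF entry restore seriousness?** The items listed in 7.3.1 are description, dates, severity, relatedness and action taken. Seriousness is not listed. Severity in 7.2.1 (mild, moderate, severe) is a different concept. The protocol therefore does not ensure that such an event is identified as serious.

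6. **Hospitalisation for alcohol intoxication.** It meets criterion c of 7.2.3. Section 7.2.4 keeps it out of incident and SUSAR reporting and does not mention SAE. *Incident* is not defined in 7.2. In 5.8, on breaking the code, the phrasing places SAEs alongside other serious incidents, which suggests that a SAE is one kind of incident. A site could read the clause either way.

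7. **Direction of error.** The SAE wording errs towards under-reporting. The unrelated-SUSAR wording errs towards over-reporting.

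**The case against.** The best defence is that the intent is clear. The bracketed AE in 7.2.3 points back to a definition without causality. The rest of 7.2.3 asks whether an event is serious and never whether it is related. Elsewhere the protocol uses SAE in that sense: section 7.1 treats any seizure as a SAE, though it notes that withdrawal can cause seizures, and in reference study 7 a SAE is separately rated for relatedness. The annual report is worded to cover all serious events. On this view a site would have to read one phrase against everything around it to under-report. The reading of intent is probably right. It shows that the 7.2.3 sentence is miswritten; it does not correct it, because 7.2.3 is the operative definition that several sites must apply alike.

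Three further objections stand and limit the point:

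- A reader might infer that serious events judged unrelated vanish from the trial record. They do not, because 7.3.1 puts every AE on the CRF whatever its attribution, judged and signed by a doctor.
- A reader might infer that alcohol-intoxication hospitalisations are exempt from SAE reporting. Section 7.2.4 does not say so; it names only incident and SUSAR. This is an ambiguity and not a waiver. Limiting expedited reporting of expected disease events can also be a legitimate choice.
- A reader might infer that the unrelated-SUSAR sentence loses events. It widens expedited reporting. Section 7.2.4 also defers to a named Directive and guidance document for SUSAR requirements.

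**Conclusion.** The definitions in 7.2.1 to 7.2.4 contradict each other and should be corrected. The defect is one of wording, but it bears on prompt safety reporting: read literally, a serious event judged unrelated falls outside the 24-hour form and the annual report while remaining on the CRF as an AE. Whether hospitalisation for alcohol intoxication must be reported as a SAE is unresolved.

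The wording governs all 380 planned patients over 91 days of treatment and the 30-day follow-up. The number of events affected cannot be derived from the protocol, because it gives no expected rate of serious events and no share judged unrelated. The conclusion assumes that sites follow 7.2.3 as written and that no SAE form or site instruction, not available here, supplies a different definition.

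The documents do not support a claim that a planned SAE comparison between arms would be biased. Section 8.2 plans descriptive safety summaries by treatment group and no test. The efficacy analysis, alpha and sample size are unaffected.

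**What to change.** Amend three sentences and align them with 7.3.1, 7.3.3 and 7.3.5:

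1. In 7.2.3, define a SAE as any AE under 7.2.1 that meets at least one of criteria a to f, regardless of causality.
2. In 7.2.4, define a SUSAR as a SAE that is both suspected to be related to the study drug and unexpected against the product information.
3. In 7.2.4, state that the natural-course clause limits expedited SUSAR reporting only, and remove or define *incident*. Such hospitalisations are then still recorded, reported to the sponsor as SAEs within 24 hours, and summarised by treatment group.

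The cost is a short amendment, a note to sites and a few more SAE forms. No visit, sample or efficacy analysis changes.

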7.2.4. Suspected unexpected serious adverse reaction (SUSAR)

A suspected unexpected serious adverse reaction (SUSAR) is a SAE of which nature or severity is not consistent with the applicable product information, that is, the SmPCs for VAR and BUP. A SUSAR may be related or unrelated to the study drug, but is unexpected. The responsibilities and requirements concerning SUSAR reporting are determined by Directive 2001/20/EC and a detailed guidance document (CT-3).

If the natural course of the disease usually causes certain symptoms, hospitalizations, etc., these will not be reported as incident or SUSAR (for example hospitalization due to alcohol intoxication).

7.3. Reporting**7.3.1. Adverse Event (AE)**

All AEs occurring during the trial that are observed by study personell or reported by the subject, will be recorded by the study coordinator on the CRF, whether or not attributed to trial medication. All reported AEs will be judged and signed by responsible medical doctor. The following information will be recorded:

description, date of onset and end date, severity, assessment of relatedness to trial medication and action taken. Follow-up information should be provided as necessary.

The Investigator's clinical judgment will decide whether or not an AE is of sufficient severity to require the participant's removal from treatment. A subject may also voluntarily withdraw from treatment due to what he or she perceives as an intolerable AE. At pre-term termination due to AE, the participant must undergo an end-of-trial assessment and be given appropriate care under medical supervision until symptoms cease, or the condition becomes stable.

7.3.2. Adverse Drug Reaction (ADR)

AEs considered related to the trial medication as judged by the medically qualified investigator or the Sponsor will be followed either until resolution, or the event is considered stable.

7.3.3. Serious Adverse Event (SAE)

All SAEs must be reported on the SAE Reporting Form to the Sponsor or delegate within 24 hours of Site study team becoming aware of the SAE.

7.3.4. Suspected Unexpected Serious Adverse Reaction

All Suspected Unexpected Serious Adverse Reactions (SUSARs) will be reported by the Sponsor to the relevant Competent Authority (CA), to the Ethics Committee and all participating Investigators. Fatal and life-threatening SUSARs, this will be reported no later than 7 calendar days after the Sponsor or delegate is first aware of the reaction. Any additional relevant information will be reported within 8 calendar days of the initial report. All other SUSARs will be reported within 15 calendar days.

This is an investigator-initiated study where the PI lacks the ability to report directly into the European database of side effects (the EudraVigilance database). The CA, in this case Swedish Medical Products Agency, will provide the service of reporting SUSARs to the EudraVigilance system. SUSARs will be reported by the Sponsor/PI via the CIOMS-form to the CA by sending it to [contact]

7.3.5. Annual Safety Report

A safety report will be completed by Sponsor once a year and sent to the CA and the Ethics Committee. The document will define the time period reported and summarize all occurred serious events (SAEs and SUSARs). The safety report should also always include a summary assessment of the safety of subjects that are still included in the trial and whether the benefit-risk assessment changed since the study was approved.

7.4. Procedures in case of emergency, overdose or pregnancy

VAR and BUP are contraindicated in pregnant or nursing women. Thus pregnancy or nursing infant(s) as well as women of childbearing age not using a contraceptive are exclusion criteria and accordingly not included in the study.

If an emergency, an overdose or pregnancy occurs during the course of the study, the subject must be withdrawn from study medication immediately and the incidence notified to the Sponsor without delay. The patient will be followed up during the entire course of the sequele. In case of pregnancy, the pregnancy and lactation period, with prenatal and neonatal outcomes recorded even if completely normal and without Adverse Events

Emergency phone number

Emergencies including overdoses will be handled by an Emergency card and a safety call center. The central call center will be serviced by professions that can provide core information to take immediate action for each emergency. The call center will be serviced 24 hrs a day by the investigational staff at the coordinating center.

Patient Emergency Card

The study subject should carry an emergency card during the trial. The card contains information about the medications in the study, investigators responsible for the study and contact information. In case of an emergency and when breaking the code is of medical importance, the responsible medical doctor can call the call center for breaking the specific code of the study participant (see Appendix 3 for Patient Emergency Card).

8. STATISTICS

8.1. Sample size calculation

The power analysis is based on two independent primary hypotheses;

- B-PEth differs significantly between VAR and BUP in combination and alone versus placebo
- Proportion of heavy drinking days (HDD) differ significantly between VAR and BUP in combination and alone versus placebo

Concerning B-PEth, we assume that we can use ordinary t-tests based on normal distribution, with $\alpha=0.025$, $1-\beta=0.80$ and using a standard deviation of 0.8 (previous results from (de Bejczy et al., 2015)). Recruiting 320 patients, randomized in 4 groups of 80 each, we get a detectable effect of 0.35 umol/l and a Cohen's d of 0.44. With regards to HDD, we assume that we can use ordinary t-tests based on normal distribution, with $\alpha=0.025$, $1-\beta=0.80$, using a standard deviation of maximum 0.35 (previous results from (Litten et al., 2013)). Recruiting 360 patients, randomized in 4 groups of 90 each, we get a detectable effect of 15% and a Cohen's d of 0.43. Hence, a sample size of approximately 360 patients should be randomized.

Drop-out rate

Based on prior studies (de Bejczy et al., 2015) with similar design and outcome, the drop-out rate is estimated to approx. 20 % between screening and randomization and approx. 6.5% for randomization to subjects included in modified ITT. To balance the drop-out, 380 subjects are estimated for randomization to reach 360 subjects in the modified ITT.

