3.2. Rationale for study design

This trial assesses the efficacy of the established smoking cessation agents, VAR and BUP, on the new indication, AUD. The study assesses VAR and BUP alone and in combination, and is designed with 4 parallel groups to address the following hypotheses:

- Combination treatment with VAR and BUP reduces B-PEth levels and HDD from baseline and significantly more than placebo. The effect size, as measured by B-PEth, for the combined treatment is hypothesized to be 0.5-0.6 (Cohen's d).
- BUP reduces B-PEth levels from baseline and HDD from baseline and significantly more than placebo. The effect size, as measured by B-PEth, is hypothesized to be approximately 0.35 (Cohen's d).
- VAR reduces B-PEth levels from baseline and HDD significantly more than placebo. The effect size, as measured by B-PEth, is expected to be approximately 0.35 (Cohen's d).

Rationale for two primary End Points

Regulatory agencies will consider only one specific primary objective. The two primary endpoints fulfill regulatory requests independently and separately. HDD fulfill requirements for application of marketing approval. The biological marker is used to assess the reliability of PEth as End Point measure.

Rationale for the study design

A parallel group design will be used. A crossover design is not an option due to the risk that the beneficial effects of the first treatment will carry over into the second treatment period. The duration of a parallel-group trial is often shorter because only one treatment period is involved (yet a larger study group is needed). As in [name] et al. (de Bejczy et al., 2015) and Litten et al. (Litten et al., 2013) it is estimated that 12 weeks steady state duration will be adequate for detecting tentative effects, as measured by B-PEth and HDD, and at the same time be manageable for the participants, thus optimizing study compliance.

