8.2. Statistical analysis

The main hypotheses that will be tested in a hierachial fashion are:

- Combined treatment with VAR and BUP reduces blood concentrations of B-PEth from baseline and significantly more than double-placebo, VAR or BUP alone.
- VAR reduces B-PEth from baseline and significantly more than double-placebo.

The ANCOVA analysis will compare the mean values of the variable in question for the different treatment groups hierachially. Regulatory agency will consider only one specific primary objective and since the two primary endpoints fulfill regulatory requests independently and separately, no adjustment for multiplicity has been done. As testing between treatments are performed in a hierachial fashion, no adjustment for multiple testing has been done.

The SAS® software, version 9.2 or higher, will be used to produce all of the statistical outputs.

All efficacy and safety variables will be presented using descriptive statistics and graphs as appropriate.

Safety measures will be summarized descriptively using the safety analysis set. Continuous variables will be presented with descriptive statistics (n, mean, standard deviation [SD], median, min, max), within treatment group. Categorical variables will be summarized by treatment group in frequency tables (number of patients and percentage). The denominators for all percentages will be defined as the number of non-missing values for each variable within the analysis set. Percentages will be presented with 1 decimal place.

Primary efficacy variables

- **B-PEth**

One of the primary outcomes will be level of PEth measured in blood.

The primary efficacy variable, B-PEth, is calculated as the mean value over the 8-week steady state active treatment period visit 4 – visit 8 (Day21-Day77) compared to baseline. The data is analyzed as the within patient difference. Day78-Day91 is omitted in the analysis period due to the tendency of drop-out and non-compliance at the end of a study period. Day 0-Day21 is omitted in the analysis due to titration of IMP and optimal timeframe of B-PEth analysis.

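### Section 8.1 applies one 80% power figure (B-PEth d about 0.44) to VAR alone and BUP alone, for which 3.2 expects d about 0.35, and gives no power for combination versus single drug

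*Protocol*

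**What the plan says.** Section 8.1 bases the power analysis on two hypotheses. The one for B-PEth reads "B-PEth differs significantly between VAR and BUP in combination and alone versus placebo", so VAR alone and BUP alone belong to what is being powered. The inputs are an ordinary t-test, alpha 0.025 with no statement of sidedness, power 0.80, and "using a standard deviation of 0.8". The result is a single line: "Recruiting 320 patients, randomized in 4 groups of 80 each, we get a detectable effect of 0.35 umol/l and a Cohen's d of 0.44". The HDD calculation sets the final size: "Recruiting 360 patients, randomized in 4 groups of 90 each, we get a detectable effect of 15% and a Cohen's d of 0.43". To allow for drop-out, 380 are to be randomized (95 per arm) to give 360 in the mITT set.

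Section 3.2 states the expected effects versus placebo on B-PEth. VAR alone and BUP alone are each put at d of about 0.35, and the combination at 0.5-0.6.

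Section 8.2 lists the main hypotheses, to be tested hierarchically. The first is "Combined treatment with VAR and BUP reduces blood concentrations of B-PEth from baseline and significantly more than double-placebo, VAR or BUP alone". The second is that VAR beats double placebo. The B-PEth analysis is an ANCOVA with baseline B-PEth as a covariate.

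Section 1.2 names superiority of the combination over VAR alone as the main anticipated benefit, and confirmation of the VAR effect as the second.

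**The concern.** Three sections of the protocol do not fit together. Section 8.1 attaches 80% power to a hypothesis that includes each drug alone, while 3.2 expects single-drug effects smaller than the effect detectable at that power. The first main hypothesis of 8.2 contains contrasts with the single drugs that 8.1 does not cover.

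The mismatch is easy to miss because the number 0.35 appears in both places on different scales. In 8.1 it is 0.35 umol/L, which is d = 0.35/0.8 = 0.44. In 3.2 it is d = 0.35, which is 0.35 x 0.8 = 0.28 umol/L.

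What is at stake is how a null result is read. Someone who takes 8.1 at face value will believe the trial had 80% power for VAR alone and BUP alone at the effects expected. That reader could take a non-significant result as evidence of no effect. The same applies to combination versus VAR, which 1.2 puts first.

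**Working it through.** **Inputs.** SD 0.8 umol/L, power 0.80, alpha 0.025, and 80 or 90 per arm (8.1); 95 per arm randomized. Expected d versus placebo: 0.35 for VAR, 0.35 for BUP, 0.5-0.6 for the combination (3.2). Combination versus single drug is not stated. By subtraction on a common SD it is 0.50 - 0.35 = 0.15 to 0.60 - 0.35 = 0.25.

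**Formulas** (two equal arms of n, normal approximation):
- detectable d = (z for alpha + z for power) x sqrt(2/n)
- power = Phi(d x sqrt(n/2) - z for alpha)

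Reported figures use the noncentral t, which differs from these by about half a percentage point or less in the cases below.

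**Step 1: reproduce 8.1.** With one-sided 0.025 (the same as two-sided 0.05):
- B-PEth, n = 80: (1.960 + 0.842) x sqrt(2/80) = 0.443, and 0.443 x 0.8 = 0.354 umol/L. Noncentral t: 0.446 and 0.357. The protocol has 0.44 and 0.35.
- HDD, SD 0.35, n = 90: 2.802 x sqrt(2/90) x 0.35 = 14.6%. Noncentral t: 14.7%. The protocol has 15%.

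With two-sided 0.025 the noncentral t gives 0.393 umol/L (d 0.491) and 16.2%, which match neither stated effect. The one-sided reading is therefore used below, with the two-sided reading alongside.

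**Step 2: detectable d at each size the protocol names** (one-sided 0.025, noncentral t): 0.446 at 80 per arm, 0.420 at 90, 0.409 at 95. The expected single-drug d of 0.35 is below all three.

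**Step 3: power at the effects in 3.2.** Worked example for a single drug at n = 90: 0.35 x sqrt(45) - 1.960 = 2.348 - 1.960 = 0.388, and Phi(0.388) = 0.651. Noncentral t: 0.646. Marginal power at 90 per arm, unadjusted t-test:

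| Comparison | d | One-sided 0.025 | Two-sided 0.025 |
|---|---|---|---|
| Combination vs placebo | 0.5-0.6 | 92-98% | 86-96% |
| VAR or BUP alone vs placebo | 0.35 | 65% | 54% |
| Combination vs VAR or BUP alone | 0.15-0.25 | 17-39% | 11-28% |

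For a single drug versus placebo, one-sided, the figure is 59% at 80 per arm and 67% at 95. To show the scale of the gap, n = 2 x (2.802/d)^2 for 80% power gives about 129 per arm at d 0.35, 252 at d 0.25 and 698 at d 0.15.

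**Step 4: possible gain from the ANCOVA.** If SD 0.8 is unadjusted, the effective d is 0.35/sqrt(1 - r^2), where r is the baseline-outcome correlation. The protocol gives no r, so a range is assumed. At 90 per arm, one-sided, power is 69% at r = 0.3, 77% at 0.5 and 83% at 0.6. Reaching 80% needs r of about 0.55. If SD 0.8 is already adjusted, there is no such gain.

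**Step 5: effect of the hierarchy.** A simulation (1,000,000 runs, z-tests, two-sided 5%, 90 per arm, single drugs at d 0.35, combination at 0.5 or 0.6) gives the joint chance of a formal VAR claim. It is 63-65% if only combination versus placebo must succeed first. It is 3-12% if all three first-step contrasts must succeed. Section 8.2 does not say which applies.

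**Step 6: drop-out, a side point.** 380 x (1 - 0.065) = 355.3, or 88.8 per arm, not 360. Single-drug power becomes 64.0% instead of 64.6%.

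**The case against.** The strongest reply is that 8.1 states only a detectable effect, that this effect is computed correctly, and that nowhere does the protocol claim 80% power at d = 0.35. An expected effect below the detectable one is then a design limitation that any reader can work out. It can be added that HDD, not B-PEth, sets the sample size, that a Phase II trial need not power every contrast it tests, and that the planned ANCOVA could bring single-drug power close to or above 80%.

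The arithmetic in 8.1 is indeed sound. But 8.1 ties its one figure to a hypothesis that names the single drugs, so the conflict with 3.2 is within the document and is more than an omitted detail. That HDD sets the size does not help B-PEth, because at 90 per arm the detectable d is still 0.42.

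The ANCOVA point partly stands. It depends on an unstated correlation and on whether SD 0.8 is adjusted, and 8.1 explicitly assumes ordinary t-tests. It is a reason to state the assumption.

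Two cautions also stand. The d of 0.15-0.25 is inferred by subtracting two approximate effects on a common SD, and should be labelled as such. The 3% to 65% spread for a formal VAR claim mainly reflects the unclear gating in 8.2, and is not in itself an error in 8.1.

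**Conclusion.** The concern holds. The detectable effect in 8.1 is right, but it is presented as covering comparisons for which 3.2 expects a smaller effect, and it leaves out a comparison that 8.2 makes a main hypothesis. At the planned 90 per arm, marginal power is about 65% for VAR or BUP alone versus placebo and about 17-39% for combination versus a single drug. Combination versus placebo is not affected.

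These figures assume an unadjusted t-test, SD 0.8 and alpha one-sided 0.025. If alpha is two-sided, power is lower and the conclusion is the same. The existence of the gap is certain from the protocol's own figures. Its size for the single drugs depends on how much the ANCOVA gains, which cannot be settled without the baseline correlation and the basis of SD 0.8.

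**What to change.** Keep the sample size, endpoints and tests, and amend 8.1 as follows.

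1. The sponsor confirms and states whether alpha = 0.025 is one-sided or two-sided.
2. Replace the single B-PEth power statement with power by comparison at about 90 per arm, SD 0.8, unadjusted t-test. If one-sided: 80% power applies to d of about 0.42 (0.34 umol/L) or more; combination versus placebo about 92-98%; VAR or BUP alone versus placebo about 65%; combination versus VAR or BUP alone about 17-39%, noting that d 0.15-0.25 is implied by 3.2. If two-sided: d of about 0.46 (0.37 umol/L); 86-96%; 54%; 11-28%.
3. Say that these are marginal powers, before the hierarchy in 8.2.
4. If a gain from the ANCOVA is relied on, state the assumed baseline correlation and whether SD 0.8 is adjusted.
5. Minor: reconcile the approximate 6.5% loss, the 380 randomized and the 360 in the mITT set.

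The cost is wording only. The stated power for the single-drug and combination-versus-single-drug comparisons becomes less favourable; no more patients are needed.
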